## **11.0 Privacy/Confidentiality Issues**

During this study every attempt will be made to keep the patient's protected health information (PHI) private. Most study data will be maintained in a Vanderbilt REDCap database. Vanderbilt Redcap is a secure, web-based application for building and managing online databases. The data obtained and stored in Redcap will only be accessible by research personnel. Any data sent to non-key study personnel for statistical analysis will be de-identified (dates will be shifted using a Redcap feature). Project team members listed as Key Study Personnel with existing electronic health record (EHR) system access rights may also be granted use of REDCap Clinical Data Interoperability Services (CDIS) tools. These tools are designed to enable transfer of relevant study-related data from the Vanderbilt Research Derivative and/or directly from the EHR into REDCap. The Research Derivative is a database of clinical and related data derived from the Vanderbilt University Medical Center's (VUMC) clinical systems and restructured for research. Data is repurposed from VUMC's enterprise data warehouse, which includes data from StarPanel, VPIMS, and ORMIS (Operating Room Management Information System), EPIC, Medipac, and HEO among others. The medical record number and other person identifiers are preserved within the database. Data types include reimbursement codes, clinical notes and documentation, nursing records, medication data, laboratory data, encounter and visit data, among others. Output may include structured data points, such as ICD 9 or 10 codes and encounter dates, semi-structured data such as laboratory tests and results, or unstructured data such as physician progress reports. The database is maintained by the Office of Research Informatics under the direction of [name]. Any physical study forms (ex. consent documents, surveys) will be kept in a locked cabinet in the principal investigator's office]. All study data will be maintained for 6 years following study

completion. Following this 6-year period, the Redcap database will be archived, and all physical study forms will be disposed of in shred-it confidentiality bins.

## **12.0 Follow-up and Record Retention**

The duration of this study will last until we have enrolled and completed follow-up on 144 participants. Based on historical frequency, expected study period to accrue the expected sample size will be 2-3 years. All study data will be maintained for 6 years following study completion. Following this 6-year period, the Redcap database will be archived, and all physical study forms will be disposed of in shred-it confidentiality bins.

Statistical Analysis Plan (SAP)

Steroid Administration for Articular Fractures of the Elbow (SAFE Trial): A Randomized, Controlled Trial of Perioperative Glucocorticoids during Treatment of Intraarticular Elbow Fractures

Principal Investigator: [name]

Assistant Professor, Orthopaedic Surgery

Protocol Identification Number: 210125

Clinicaltrials.gov Identifier: NCT04738318

Version Date 03/09/2021

Statistical analysis plan

Demographics will be compared between each treatment arm in each stratification group for comparison and summary statistics for each treatment arm will be provided. If significant differences exist in patient, injury, or treatment variables, subgroup analysis will be performed. Assumptions for each variable will be assessed for normality using histograms and frequencies and cross tabulation will be tabulated for categorical and ordinal variables. If continuous data is not normally distributed, we will use non-parametric analysis methods. Graphical methods will be used to examine data distributions, identify influential observations, and perform transformations if needed. Prior to hypothesis testing, the data will be screened for errors and missing values using descriptive statistics and histograms. Suspicious values will be confirmed for accuracy and changes will be documented in an appendix. Every effort will be made to minimize missing or incomplete data. Study personnel will follow-up with all providers and patients to collect data. Data will be analyzed in a pragmatic fashion and all collected data will be analyzed.

We will use the open-source statistical package R (R Development Core Team, 2012) and Stata 16 statistical software (StataCorp LLC, 2019, College Station, TX) for analysis. An intention-to-treat analysis will be conducted including all eligible patients as originally randomized. Analysis of each primary and secondary endpoint will be performed with all patients at each follow-up time point. Interactions for fracture-type and treatment group will be modeled at each follow-up time point and if significant, each fracture-type group will be independently analyzed. Multivariable proportional odds models for the Aim 1 dependent variable, range-of-motion, will be performed and multivariable logistic regressions will be performed for Aim 2 outcomes evaluating complications and safety. The Aim 3 dependent variable is continuous MME total and will be analyzed using a multivariable proportional odds model as the total amount consumed for each patient during the post-operative course.

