### Secondary Study Questions

- b. Is perioperative glucocorticoid administration more effective in improving range of motion for certain intra-operative elbow fractures or depending on the mechanism of injury (subgroup comparison based on fracture type and high-energy or low-energy injuries)?
- c. Do patients that receive perioperative glucocorticoids have a higher surgical site infection rate?

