### **Randomization**

Patients will be randomized according to a stratified permuted block randomization with a block size of 4. Randomization will be stratified based on fracture type: radial head, distal humerus, proximal ulna, combined. Treatment A will receive glucocorticoid and Treatment B will receive placebo. There will be 9 total blocks per fracture type, for 36 patients in each fracture-type strata and an even balance in all 4 strata, for 18 in each treatment arm.

Randomization will take place after consent. A randomization allocation table will be uploaded into REDCap. Randomization will be conducted by an Orthopaedic research coordinator. The treating physician, study research coordinator and patient will be blinded to the treatment assignment.

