### **Statistical Analysis**

- a. Primary analysis
  - i. Intention-to-treat
  - ii. Baseline characteristics between treatment arms will be compared using univariate descriptive statistics.
  - iii. Primary end-point (range of motion: continuous variable) → Univariate analysis of unmatched, interval variable with two groups assuming non-normal distribution: Mann-Whitney U Test will be performed.

- iv. Secondary end-points that are dichotomous (infection, revision surgery, heterotopic ossification, and other complication) will be analyzed with a chi-square or Fisher's exact test where the assumptions for a chi-square test are not met.
- v. Secondary end-points that are nominal or ordinal (Pain score, DASH score) will be analyzed using a Mann-Whitney U Test.

b. Subgroup analysis

- i. Analysis will be performed based on fracture type and stratification will make comparison possible.
- ii. Multivariate analysis using linear regression for the interval variable (range of motion) will be performed based on:
  1. Age <65 vs Age >65
  2. Mechanism of injury (High-energy vs. Low-energy)
  3. Treatment type
  4. Time from injury to surgery

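### The SAP lets a chance baseline difference between arms decide whether subgroup analysis is run, with no variable list, interaction test or exploratory label

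*SAP*

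**What the plan says.** The SAP compares baseline data by arm inside the randomisation strata ("Demographics will be compared between each treatment arm in each stratification group for comparison") and then gives the rule: "If significant differences exist in patient, injury, or treatment variables, subgroup analysis will be performed". It states no significance level, list of variables, cut-points, interaction test or status for the results.

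Other parts of the plan bear on this:

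- Protocol 5.0, Randomization: "Randomization will be stratified based on fracture type: radial head, distal humerus, proximal ulna, combined".
- Protocol 2.0, secondary question b, asks for a "subgroup comparison based on fracture type and high-energy or low-energy injuries". These are the only two subgroup questions posed in advance.
- Protocol 10.0, Statistical Analysis, a.ii: "Baseline characteristics between treatment arms will be compared using univariate descriptive statistics".
- Protocol 10.0, a.iii, gives the primary test, which is unadjusted: "Univariate analysis of unmatched, interval variable with two groups assuming non-normal distribution: Mann-Whitney U Test will be performed".
- Protocol 10.0, b.ii, under the subgroup heading: "Multivariate analysis using linear regression for the interval variable (range of motion) will be performed based on" age, mechanism of injury, treatment type and time from injury to surgery. Fracture type is not in that list.
- The SAP's second paragraph models the interaction of fracture type with treatment at each visit and analyses fracture types separately only if it is significant. It also plans multivariable proportional odds models for range of motion, without naming covariates.

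**The concern.** A baseline test in a properly randomised trial asks whether chance produced a difference that is already known to be chance. The answer says nothing about whether the drug works differently in, say, older patients. Using it to choose subgroups lets noise add to the two questions the protocol asks.

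If the aim is to deal with imbalance, splitting is the wrong tool. It balances the variable within each level at a cost in precision, and leaves the overall comparison as it was. Adjustment for covariates chosen in advance addresses imbalance directly.

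The plan also treats like cases differently: fracture type must show an interaction before it is analysed separately, whereas a triggered variable need not. A subgroup picked by a chance imbalance could then be reported as planned, and a result significant in one level but not in the other could be taken for a real difference in benefit.

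**Working it through.** The plan gives no figure for this rule, so there is none to reproduce.

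**Inputs from the documents.** Four strata of 18 v 18, 144 patients in all (Protocol 5.0). The trigger rule and the comparison within strata (SAP).

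**Assumptions, not in the documents.** Each baseline test is at 0.05. There are k = 3, 5 or 10 independent variables. Three is the Protocol 10.0 b.ii list if treatment type means the trial arm. There is no true treatment effect.

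**Step 1: chance of at least one trigger.** If arms are compared once, 1 − 0.95^k. If they are compared in each of four strata, 1 − 0.95^(4k).

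**Step 2: chance of a trigger followed by a false-positive subgroup, for one endpoint at one visit.** This further assumes that each triggered variable is split into two levels and treatment is tested at 0.05 in each.

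- At least one false positive in two levels: 1 − 0.95² = 0.0975.
- Trigger and false positive for one baseline comparison: 0.05 × 0.0975 = 0.004875.
- Over m comparisons: 1 − (1 − 0.004875)^m, with m = k or 4k.

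| k | Trigger, once | Trigger, within strata | Trigger + false positive, once | Trigger + false positive, within strata |
|---|---|---|---|---|
| 3 | 14.3% | 46.0% | 1.5% | 5.7% |
| 5 | 22.6% | 64.2% | 2.4% | 9.3% |
| 10 | 40.1% | 87.1% | 4.8% | 17.8% |

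**Step 3: check by simulation.** Inputs were 20,000 trials per setting, 18 v 18 in four strata, a t-test trigger and a Mann-Whitney test in each level. For k = 3, 5 and 10, trigger plus false positive was 1.4%, 2.2% and 4.5% once. Within strata it was about 5%, 8% and 14-16%, depending on whether the split used all patients or only the triggering stratum.

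**Step 4: departures from independence.** For k = 5 and 10:

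- Variables correlated 0.5: 2.0% and 3.7% once; 7-8% and 13-14% within strata.
- Binary variables with Fisher's exact test: 1.5-1.8% and 3.1-3.5% once; 4-6% and 8-11% within strata.

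**Step 5: effect of an interaction test.** One test at 0.05 per triggered variable replaces 0.0975 by 0.05. If arms are compared once, 1 − (1 − 0.0025)^k gives 1.2% (k = 5) and 2.5% (k = 10), about half the Step 2 figures.

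**The case against.** The strongest reply is that the SAP never says patients are split. Protocol 10.0 files its multivariable regression under the subgroup heading, so the triggered analysis may be, at least in part, a covariate-adjusted model. That stands as a real ambiguity. On that reading the Step 2 figures fall away and only the trigger rates remain. It does not rescue the rule, because whether the analysis is run would still depend on a chance baseline test.

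Three further points also stand:

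- The SAP does not define significance for baseline data, and the protocol calls the comparison descriptive. The 0.05 level is therefore an assumption.
- The chance argument covers pre-randomisation variables only. The rule also names treatment variables, some of which may be settled later; the calculation treats every variable as null.
- The protocol already ranks subgroup questions as secondary and keeps them apart from the primary analysis.

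A reader might infer more than the documents support:

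- *That the primary result is compromised.* It is not. The intention-to-treat comparison is run whatever the baseline tests show, so its type I error is unchanged.
- *That false subgroup findings could approach one in two.* Over two motion arcs and four visits, with an assumed correlation of 0.6, simulation gives 49-53% for ten variables tested within strata. Much of that is multiplicity over endpoints and visits: a single interaction test always run on the same eight outcomes gives about 22%.
- *That a uniform benefit would often look confined to one subgroup.* At SD 17 degrees and 36 v 36 per level, one level is significant and the other not in 43% or 23% of splits if the true benefit is 10 or 12.5 degrees. That applies to any split, and those effects are not in the plan. At the planned 25 degrees it is about 0% in a full-sample split.

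**Conclusion.** The concern holds in a limited form. The SAP ties subgroup analysis to a test that, for pre-randomisation variables, detects only chance, and it lacks the interaction step that the same document applies to fracture type. A trigger is likely if arms are compared within strata, which is the comparison the SAP describes for demographics (46-87%), and less so if they are compared once (14-40%). The chance that this ends in a false-positive subgroup is modest: about 1.5-5% or 6-18% per endpoint and visit, on the two-level reading, and lower for correlated or binary variables. All of this rests on the assumed 0.05 level and 3 to 10 independent variables.

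The damage is confined to secondary claims about who benefits. The sentence should be changed because a better method is available at little cost; the trial's main comparison is not in doubt.

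**What to change.** 1. Delete the trigger sentence. Report baseline data by arm, and by arm within fracture type, as summary statistics without p-values, in line with Protocol 10.0 a.ii.
2. Name the covariates of the SAP's range-of-motion proportional odds model in advance, whatever imbalance is seen: fracture type, age, mechanism of injury and time from injury to surgery. Time to surgery may be settled after randomisation, but the blinding protects it from influence by allocation: "The treating physician, study research coordinator and patient will be blinded to the treatment assignment".
3. State in the protocol what treatment type means in 10.0 b.ii: the trial arm or the surgical treatment.
4. Limit planned subgroups to fracture type and mechanism of injury, each tested by its interaction with treatment. Label any other subgroup post hoc.

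The adjusted model complements the unadjusted Mann-Whitney test; it does not correct it, and the primary test stays as it is.

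The cost is a few sentences of SAP text and one protocol clarification, with no new data and no change to the sample size. The downside is that exploring imbalanced variables is no longer a planned analysis, though it can still be done and labelled post hoc.

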## 2.0 Hypothesis and Specific Aims

### Primary Study Questions

- a. For adult patients (>18yo) who sustain intra-articular elbow fractures (radial head, proximal ulna, distal humerus, or combined) that undergo operative fixation, does perioperative glucocorticoid administration (IV intra-operative followed by a post-operative oral taper course) improve post-operative range of motion (flexion/extension and pronation/supination) compared to a placebo?

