### Hypothesis

1. Alternative: In adult patients with intra-articular elbow fractures, peri-operative dexamethasone administration will improve post-operative active range of motion early ( $\leq 6$  weeks) and at final follow-up ( $\geq 6$  months).
2. Null: In adult patients with intra-articular elbow fractures, peri-operative dexamethasone administration will not improve post-operative active range of motion early or at 6 month follow-up.

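### No primary arc, visit or success rule is named for range of motion, so up to eight tests share an alpha of 0.05 meant for one

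*SAP*

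**What the plan says.** - **Endpoint.** Protocol 10.0, Statistical Analysis, item a.iii, reads "Primary end-point (range of motion: continuous variable", with no arc and no visit. For this endpoint it states that a "Mann-Whitney U Test will be performed".
- **Arcs.** The primary question in protocol 2.0 asks whether treatment will "improve post-operative range of motion (flexion/extension and pronation/supination) compared to a placebo". The two arcs are not ranked.
- **Visits.** Protocol 6.0, Follow-up Clinic Visits, collects both arcs at 2 weeks, 6 weeks, 3 months and 6 months.
- **Hypothesis.** The alternative in protocol 2.0 is that "peri-operative dexamethasone administration will improve post-operative active range of motion early" (defined as up to 6 weeks) "and at final follow-up" (6 months or later). The null is that treatment "will not improve post-operative active range of motion early or at 6 month follow-up". Neither names an arc.
- **SAP.** "Analysis of each primary and secondary endpoint will be performed with all patients at each follow-up time point". For the first aim it adds: "Multivariable proportional odds models for the Aim 1 dependent variable, range-of-motion, will be performed".
- **Sample size.** Protocol 10.0, Sample Size Justification, sizes one flexion/extension comparison at 90% power and alpha 0.05. It names no visit and does not call that arc primary.

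**The concern.** Two arcs at four visits make eight comparisons, and nothing says which of them are confirmatory. The arc, the visit and the rule for success could all be chosen after the results are seen. An alpha of 0.05 limits the error of one test; it does not limit the chance that at least one of several tests succeeds by luck.

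The hypothesis offers a candidate rule by joining early and final benefit with *and*. It leaves three things open: the arc, which of the two early visits (2 or 6 weeks) counts, and the null. Worded with *or*, the null can mean either that benefit is not shown at both times or that it is absent at both.

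The test is a further open choice, since the protocol gives a rank test and the SAP a multivariable ordinal model.

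**Working it through.** **Reproducing the plan's figure.** Inputs from protocol 10.0: difference 25 degrees, SD 17, power 90%, alpha 0.05. A two-sample t test, two-sided, with 11 per arm has noncentrality (25/17) × √(11/2) = 3.45 on 20 degrees of freedom, giving power 90.6%. This matches the stated 11 + 11 = 22. One-sided testing would need only 9 per arm, so each test is taken as two-sided at 0.05, which allows a false claim of benefit in 2.5%.

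**Independent tests (no effect anywhere).**

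| Tests that may count | At least one false positive | False claim of benefit |
|---|---|---|
| 8 (two arcs, four visits) | 1 − 0.95^8 = 33.7% | 1 − 0.975^8 = 18.3% |
| 6 (two arcs at 2 weeks, 6 weeks, 6 months) | 1 − 0.95^6 = 26.5% | 1 − 0.975^6 = 14.1% |
| 2 (two arcs at 6 months) | 1 − 0.95^2 = 9.8% | 1 − 0.975^2 = 4.9% |

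**Correlated tests.** Repeated measures on one elbow are correlated, so the values above are upper bounds. The documents give no correlations; those below are assumptions. Each setting used 1,000,000 draws of eight z statistics. In the first four settings the correlation between two tests is the visit correlation times the arc correlation; the last two use one common value.

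| Visit/arc correlation | Any of 8: any / benefit | Six tests: any / benefit | Two arcs at 6 months: any / benefit |
|---|---|---|---|
| 0.5/0.3 | 28.1% / 14.3% | 23.0% / 11.6% | 9.6% / 4.8% |
| 0.7/0.3 | 23.8% / 12.1% | 20.2% / 10.2% | 9.5% / 4.8% |
| 0.8/0.5 | 20.0% / 10.0% | 17.4% / 8.7% | 9.1% / 4.6% |
| 0.9/0.7 | 15.2% / 7.6% | 13.7% / 6.8% | 8.4% / 4.2% |
| common 0.8 | 15.8% / 7.9% | 13.9% / 7.0% | 7.8% / 3.9% |
| common 0.9 | 12.0% / 6.0% | 10.9% / 5.4% | 7.1% / 3.5% |

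**The *and* rule, either arc counting at each time (false claims of benefit).**

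| Situation | Six settings | Independent |
|---|---|---|
| No effect anywhere | 1.7-3.1% | 0.5% |
| True 6-month effect, always detected, none early: 2 arcs × 2 early visits can supply the early claim | 4.7-8.5% | 1 − 0.975^4 = 9.6% |
| True early effect, none at 6 months: 2 arcs can supply the 6-month claim | 3.5-4.8% | 1 − 0.975^2 = 4.9% |
| Flexion/extension only, both early visits kept, true 6-month effect only | 3.5-4.6% | 1 − 0.975^2 = 4.9% |

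The last row shows that naming the arc is not enough; the early visit must be named too. In the first row correlation raises the rate, so independence is not an upper bound there.

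**Effect of the remedy on power.** Evaluable patients with strata pooled: 72 per arm × 0.8 = 57.6, taken as 57. With SD 17 and a t test, the difference detectable with 90% power is 10.4 degrees at 0.05 and 11.3 at 0.025 (about 10.7 and 11.6 for Mann-Whitney, using efficiency 3/π). If both arcs must succeed at 0.05 each, 90% joint power needs 11.1-11.4 degrees per arc for arc correlations from 0.7 down to 0. Applying SD 17 to rotation and to the pooled strata is an assumption.

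**The case against.** The documents narrow the choice more than a count of eight suggests. The sample size uses flexion/extension, and the hypothesis leaves out the 3-month visit. The *and* rule is the reading nearest the text, and with no effect anywhere it keeps false claims at 0.5-3% with either arc, or 0.8-1.8% across the six settings if only flexion/extension counts. The 4.7-8.5% figure lets early benefit in one arc combine with 6-month benefit in the other. If the same arc must succeed at both times and only flexion/extension has a 6-month effect, the rate is 3.8-5.2%.

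These points are correct, but they do not remove the problem. No text calls flexion/extension primary, and the primary question gives both arcs equal standing. The SAP analyses every visit and states no decision rule. Even the stricter same-arc reading exceeds 2.5%.

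Three limits stand:
- The exact rates depend on assumed correlations, so the direction is firmer than the size.
- The rank test and the ordinal model can be read as unadjusted and adjusted analyses of one question, and none of the error rates above includes that choice. It still has to be settled which is primary.
- The protocol sizes each fracture type, so pooling the strata resolves a further open point. The SAP's reference to all patients supports pooling. At 14 per arm within one stratum (18 × 0.8 = 14.4), moving from 0.05 to 0.025 shifts the detectable difference from 21.6 to 23.8 degrees, still under 25.

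**Conclusion.** The concern holds and must be fixed before unblinding: the plan as written does not deliver its stated alpha of 0.05. If any of the eight comparisons may be claimed, at least one false positive occurs in 12-28% of trials with no effect and a false claim of benefit in 6-14%. Restricting the choice to the visits in the hypothesis gives 11-23% and 5-12%. The *and* rule gives acceptable or nearly acceptable error when there is no effect at all, but not when benefit is real at only one of the two times. These figures assume two-sided tests at 0.05 and the correlations listed. That no arc, visit or rule is designated is a matter of text and rests on no assumption.

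**What to change.** In protocol 10.0 and the SAP, before unblinding:

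1. Name one primary comparison. The natural choice is the active flexion/extension arc at 6 months, all strata pooled, two-sided 0.05: it is the arc used for the sample size, at the final time point of the hypothesis.
2. Make the rotation arc and the other visits secondary, reported as estimates with confidence intervals.
3. If early benefit is to remain a formal claim, either test in a fixed order (for example flexion/extension at 6 months, then at 6 weeks, each at 0.05), or require both to succeed at 0.05 each. In either case name the arc and the single early visit.
4. If both arcs stay primary at 6 months, state whether either suffices (0.025 each, or Holm) or both must succeed (0.05 each).
5. State whether the Mann-Whitney test or the proportional odds model is the primary analysis.
6. Reword the null and alternative in protocol 2.0 to match.

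The cost is wording only, with the sample size unchanged. With one primary comparison nothing is lost in power; letting either arc suffice raises the detectable difference per arc by about 0.9 degrees. The downside is that an isolated early gain, or a gain confined to a non-primary arc, could no longer be claimed as the primary result.

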### **Screening Form**

Once the patient has signed the informed consent document, the study team will document subject eligibility by completing the REDCap Screening Form. This step will ensure only eligible patients are included in the study. The REDCap screening form will be completed prior to randomization activities.

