### **Noncompliance**

All patients will be evaluated based on an intention-to-treat analysis. If there is noncompliance to the medicine home taper course indicating cross-over from the treatment arm to the control arm, the overall dose of glucocorticoid will be noted, and patients will be analyzed in their original randomization arm.

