## **10.0 Statistical Considerations**

### **Sample Size Justification**

Prior studies suggest Flexion/extension arc after intra-articular fracture  $\sim 105^\circ$ . Difference suggested by prior retrospective study with dexamethasone shows potential improvement ( $\delta$ ) of  $27^\circ$  (avg post-operative AROM  $132.5^\circ$ ). Conservatively, will attempt to see an improvement of  $25^\circ$  ( $\delta$ ). Average standard deviation from literature of post-operative intra-articular elbow fractures range of motion is  $17^\circ$  ( $\sigma$ ). A total of 22 patients are needed (11 treatment and 11 control) to be able to reject the null hypothesis with 90% power and  $\alpha = 0.05$ . Assuming a 20% loss to follow-up based on prior studies ( $\sim 10\%$ ) + non-compliance of six-day home taper course. As we are stratifying our treatment and control groups based on fracture type, we will need 18 patients in each treatment arm for each fracture and 18 patients in each control arm.

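### Range of motion is analysed visit by visit with no method for missing values, so patients lost before 6 months drop out of the 6-month comparison, which is biased if loss relates to motion differently in the two arms

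*SAP*

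**What the plan says.** **Analysis set.** The SAP says: "An intention-to-treat analysis will be conducted including all eligible patients as originally randomized". The protocol, section 6.0 (Noncompliance), says: "All patients will be evaluated based on an intention-to-treat analysis". Non-compliers with the taper stay in their randomised arm. On timing of the eligibility check, the protocol's Screening Form section says: "The REDCap screening form will be completed prior to randomization activities".

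**Analysis by visit.** The SAP says: "Analysis of each primary and secondary endpoint will be performed with all patients at each follow-up time point". It also models the interaction of fracture type and treatment at each time point. For range of motion, protocol section 10.0 names a Mann-Whitney test and a linear regression, and the SAP names proportional odds models. None is described as a repeated-measures analysis.

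**Missing data.** The SAP screens for missing values, has staff follow up with providers and patients, and adds: "Every effort will be made to minimize missing or incomplete data" and "Data will be analyzed in a pragmatic fashion and all collected data will be analyzed". Neither document names an imputation method, a missingness assumption or a sensitivity analysis.

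**Measurement.** Protocol section 6.0 has the treating surgeon measure active motion with a goniometer at 2 weeks, 6 weeks, 3 months and 6 months. If a visit is missed, the coordinator tries phone, mail or REDCap.

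**Expected loss.** The sample size section says: "Assuming a 20% loss to follow-up based on prior studies". The same sentence goes on to make the figure up of about 10% loss plus non-compliance with the home taper.

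**The concern.** A rank test or a single-visit regression needs an outcome value for every patient it includes. A patient measured at 2 weeks, 6 weeks and 3 months but not at 6 months contributes nothing to the 6-month result, although three informative readings are on file. The promise to analyse all patients at every time point therefore cannot be kept once anyone is lost.

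The missed-visit fallback can recover a pain score or a QuickDASH, but not a surgeon's goniometer reading. The outcome that matters most is the hardest to retrieve. Six months is also one of the two time points in the hypothesis and the last scheduled visit, where loss accumulates.

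What is at stake is bias. Patients whose elbow does well, or badly, may be less likely to return. If that tendency differs by arm, the patients still under observation at 6 months are no longer the groups that randomisation formed.

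**Working it through.** **1. The plan's own figure.** Inputs from protocol section 10.0: difference 25 degrees, SD 17 degrees, power 90%, alpha 0.05 (two-sided assumed, since sidedness is not stated). The exact t-test has power 0.875 at 10 per arm and 0.906 at 11 per arm, so the stated 11 per arm (22 in total) is reproduced.

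**2. How much loss to expect.** Inflating once for 20% gives 11 / 0.8 = 13.75, or 14 per arm. Inflating twice gives 11 / (0.8 × 0.8) = 17.2, or the plan's 18. The arithmetic therefore does not settle what the 20% stands for. Its wording combines about 10% loss with non-compliance, and non-compliers stay in the analysis and need not lack a 6-month value. Missing outcomes are then plausibly 10% to 20%: 0.10 × 144 = 14.4 and 0.20 × 144 = 28.8, or about 14 to 29 patients. That leaves about 65 or 58 of 72 per arm.

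**3. Precision is not the problem.** For 25 degrees, power is about 96% in one stratum with 14 per arm, and above 99.9% for the pooled comparison at 58 per arm.

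**4. Bias, by formula.** Suppose loss depends on outcome in one arm only. Then

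bias = fraction missing × (mean of completers − mean of non-completers).

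The standard error is 17 × √(2 / n), with n = 64.8 or 57.6 per arm, which gives 2.99 or 3.17 degrees. The gaps below are assumptions. The last two columns give the chance that a two-sided 5% test rejects when there is no true effect.

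| Gap (degrees) | Bias, 10% missing | Bias, 20% missing | Rejects, 10% | Rejects, 20% |
|---|---|---|---|---|
| 10 | 1.0 | 2.0 | 6.3% | 9.7% |
| 17 | 1.7 | 3.4 | 8.8% | 18.9% |
| 25 | 2.5 | 5.0 | 13.3% | 35.2% |

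**5. Bias, by simulation.** From the documents: 72 per arm and SD 17. Assumed: correlation 0.7 between visits, true difference 10 degrees, and logistic loss at 6 months depending on 3-month motion. Each scenario used 1,000 to 1,500 simulated trials. The visit-wise mean difference is compared with an arm-specific regression of the 6-month value on the three earlier visits, which stands in for a longitudinal model.

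| Loss depends on 3-month motion | Visit-wise estimate (share missing) | Using earlier visits |
|---|---|---|
| Same direction, relative to own arm | about 10 | about 10 |
| Same direction, on a common scale | 9.1 to 9.4 (21%), 9.5 (12%) | about 10 |
| One arm only | 7.4 (21%), 8.0 (19%), 8.5 to 8.8 (11% to 12%) | about 10 |
| Opposite directions | 4.9 (25%), 5.6 (21%), 7.3 (12%) | about 10 |

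In the one-arm and opposite rows, good movers leave the treated arm, which shrinks the estimate; reversing the directions inflates it. With no true effect and opposite directions, the Mann-Whitney test rejects 26% of the time at 21% missing and 12% at 10% missing, against a nominal 5%.

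**The case against.** **The word *eligible*.** A reader might infer that the SAP excludes some patients after randomisation. The documents do not support that. Eligibility is recorded before randomisation, radiographs confirming an intra-articular injury are an inclusion criterion, the protocol applies intention-to-treat to all patients, and no rule for later exclusion appears anywhere. What stands is an ambiguity: the SAP does not say that a patient found ineligible after randomisation, or not operated on, is kept.

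**The 20%.** A reader might take this as the plan's own forecast of missing outcomes. It is not clearly that, because non-compliance is part of it. The range of 10% to 20% is the fair reading.

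**The size of the bias.** The 4.9-degree result could be read as the expected damage. It needs opposite loss patterns in the two arms and 25% missing, which is above even the 20% reading. Patient and treating physician are blinded and the packaging is identical, so opposite patterns are possible but not the ordinary case. With the same pattern in both arms the bias is under 1 degree, against a planned difference of 25. The simulation also lets loss depend only on a recorded visit, so the method using earlier visits recovers the truth by construction. The estimates in the table are mean differences, not results of the planned rank or ordinal analyses.

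**Existing safeguards and choice of method.** The plan does commit to chasing missing data, and its rank and ordinal methods were chosen with non-normal motion in mind. Both points are fair. The first does not recover a goniometer reading from a patient who does not attend. The second bears on which remedy to choose.

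**Conclusion.** The concern holds in a limited form. As written, each visit's range-of-motion analysis uses only patients measured at that visit, no missing-data method is named, and so the stated analysis of all patients is not delivered. With about 14 to 29 of 144 patients likely to lack a 6-month value, bias arises mainly when loss relates to motion differently in the two arms. It is then roughly 1 to 3 degrees if only one arm is affected, and about 3 to 5 degrees in the extreme case, on an assumed true difference of 10. If both arms behave alike, it is under 1 degree. These figures rest on the assumed correlation, true difference and loss mechanisms, none of which the documents give.

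Dropping readings already collected is avoidable at little cost, so the SAP should be changed. The flaw is not fatal, and it is not a demonstrated exclusion of randomised patients.

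**What to change.** 1. Analyse range of motion in one longitudinal model over 2 weeks, 6 weeks, 3 months and 6 months, with arm by visit and fracture type. Take both the early (6 weeks or before) and the 6-month arm differences from it, since the hypothesis names both.
2. To keep the planned rank or ordinal approach, use an ordinal longitudinal model instead, or impute missing values several times from the earlier visits within arm and then fit the planned proportional odds model.
3. Add a delta-based sensitivity analysis: shift the imputed values over a range stated in advance, applied to each arm in turn, and report where the conclusion changes.
4. As a clarification, replace "including all eligible patients as originally randomized" with wording that covers all randomised patients in their assigned arm, to match the protocol's Noncompliance section.
5. State separately how much of the 20% allowance is loss of the outcome and how much is non-compliance.

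The cost is SAP wording and some extra programming, with no new data. It should be done before unblinding, so that the method is not chosen in view of the results. The drawback is that the main model assumes missingness is explained by the earlier visits; the sensitivity analysis in step 3 shows how far the result depends on that.
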